Patients will be pre-medicated with Midazolam. Routine monitoring will be performed including electro-cardiography, non-invasive blood pressure monitoring, heart rate oxygen saturation and end-tidal carbon dioxide and capnograph will be performed. General anesthesia will be induced with Propofol 1-2 mg/kg and analgesia will be provided with Fentanyl 2 mcg/kg. General anesthesia will be maintained using the Sevoflurane titrated to effect as determined by the anesthesia team caring for the patient. Rocuronium will be administered during the duration of the case to provide muscle relaxation for the duration of the procedure, with an induction dose of 0.6 mg/kg and titrated to 1-2 twitches assessed by continuous twitch monitor. Reversal of neuromuscular blockade will be achieved using 0.06 mg/kg of Neostigmine and 0.012mg/kg of Glycopyrrolate or 2mg/kg of sugammadex.

Possible allergic type reactions of receiving bupivacaine include urticaria, pruritis, erythema, angioedema, tachycardia, sneezing, nausea, vomiting, dizziness, and syncope. Overdosage or rapid absorption lead to systemic toxicity manifestation that need immediate counter measures related to the central nervous system and cardiovascular system. There is also risk of nerve injury given the location of the regional block. Routine precaution is taken by the surgical and anesthesia team to avoid overdosing. Any reactions or overdosing will be managed accordingly. The study will not alter the subjection to possible adverse reaction as this is an observational study.

Data Collection Procedures:

As this is an observational (prospective cohort) study, there will be no randomization or blinding done. We will be observing the patient's post op pain scores and amount of pain medication used

Postoperatively, patients will be transferred to the PACU for monitoring. The amount, timing and type of additional pain medications necessary at 1 and 3 hours after surgery will be recorded. Pain levels will be documented at the same 1- and 3-hours intervals, and scored utilizing a 1-10 Numeric Rating Scale (NRS). The NRS is a verbal assessment, asking patients to quantify their pain on 1- 10 scale. It has previously been shown in studies to be a simple, valid alternative to the visual analog scale (VAS).

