Study subjects will receive a telephone call 24 hours after surgery and asked about how much additional medication they have taken for pain control, as well as their pain level utilizing the same 1-10 NRS assessment.

Our primary outcome is difference in pain scores at 3 hours. Our secondary outcome is difference in pain scores, at 1 hour, 24 hours, difference in additional medication taken orally for pain control, and adverse effects if any.

Sociodemographic and clinical data of study subjects will also be obtained, including age, body mass index, history of abdominal and pelvic surgeries, history of pelvic adhesive diseases such as endometriosis, duration of surgery, and duration of stay postoperatively in PACU.

Data Analysis: the mean difference between pain scores at 1 hour, 3 hour, and 24 hour, and the difference in the amount of oral pain medication used will be assessed as below.

Expected Outcomes: Our study aims to show that patients receiving a preoperative QL block will have lower post-operative pain scores and will need less oral pain medication

REFERENCES:

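### Adverse effects are a secondary outcome, but no described assessment asks about them, no source record is named, and the Data Analysis sentence leaves them out

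*Combined protocol and SAP*

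**What the plan says.** All references are to the combined protocol and SAP.

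- **Outcome.** Under Data Collection Procedures, the list of secondary outcomes ends with "and adverse effects if any". No definition, time window or source is attached.
- **1 and 3 hours, in PACU.** "The amount, timing and type of additional pain medications necessary at 1 and 3 hours after surgery will be recorded". Pain is scored at the same two times, and "The NRS is a verbal assessment", so someone already speaks to the patient.
- **24-hour telephone call.** Patients are "asked about how much additional medication they have taken for pain control, as well as their pain level". No other question is described.
- **Other data.** A list of sociodemographic and clinical variables follows. It is worded as a list of examples and does not mention adverse effects.
- **Risks.** The Design section states: "Possible allergic type reactions of receiving bupivacaine include urticaria, pruritis, erythema, angioedema, tachycardia, sneezing, nausea, vomiting, dizziness, and syncope". It then mentions systemic toxicity affecting the nervous and cardiovascular systems, and adds: "There is also risk of nerve injury given the location of the regional block". It says that reactions will be managed, but not that they will be recorded as study data.
- **Blinding.** Data Collection Procedures states that "there will be no randomization or blinding done".
- **Analysis.** The Data Analysis sentence names pain at 1, 3 and 24 hours, "and the difference in the amount of oral pain medication used will be assessed as below". What follows is a statement of expected outcomes and the reference list.

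**The concern.** An outcome needs a definition, a source and a summary. As described, this one has none of the three.

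The gap is clearest between leaving PACU and the 24-hour call. Nausea, dizziness or itching in that period would reach the study only if a patient volunteered it or a clinician happened to chart it. Symptoms that were neither asked about nor charted cannot be recovered at analysis.

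The arms could also be captured differently. The risk text is written about bupivacaine, and the only bupivacaine the plan describes is in the block. Staff who use that text as an informal prompt would look harder in the block arm. Conversely, Background and Significance gives opioid side effects as a reason for using regional blocks, so staff with that in mind could look harder in the control arm. The plan does not say whether opioid side effects count, so the same episode of nausea could be recorded in one patient and ignored in another.

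Two readings are at stake: a low count taken as reassurance, and a between-arm difference that is really a difference in who was asked.

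**Working it through.** The plan gives no adverse-effect rate, capture rate or sample size, so there is no figure to reproduce. The check is a comparison of the outcomes with the data items and the analysis sentence.

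**Step 1: does any described assessment collect adverse effects?**

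| Assessment | Described items | Adverse-effect item |
|---|---|---|
| 1 h, PACU | pain medication, pain score | none |
| 3 h, PACU | pain medication, pain score | none |
| 24 h call | pain medication, pain score | none |

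Result: 0 of 3.

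**Step 2: which secondary outcomes does the Data Analysis sentence name?**

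| Secondary outcome | Named |
|---|---|
| Pain at 1 h | yes |
| Pain at 24 h | yes |
| Oral pain medication | yes |
| Adverse effects | no |

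Result: 3 of 4. The sentence refers forward to analysis text that is not in the supplied document. That text may have been lost when the PDF was read. The sentence's own list still leaves out adverse effects, and Step 1 does not depend on it.

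**Step 3: could events be captured another way?** In part. The Design section describes ECG, blood pressure, heart rate, oxygen saturation and capnography during anesthesia, and Data Collection Procedures has patients monitored in PACU. The block is given after induction and before surgery, so an early reaction falls within the monitored period. Tachycardia or cardiovascular toxicity would ordinarily show there. But no record from that period is named as a study source, and nothing says that records are reviewed alike in both arms. After PACU, the only study contact described is the call in Step 1.

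**Step 4: which way could uneven capture push the result?** Let p be a true risk that is equal in both arms, and let s be the fraction of patients with an event whose event is recorded. The observed risk is p × s in each arm, so the observed ratio is s(block) / s(control), whatever p is. The inputs below are assumptions, not taken from the documents:

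- 90% and 60%: 0.90 / 0.60 = 1.50
- 60% and 90%: 0.60 / 0.90 = 0.67
- 60% in both: 0.60 / 0.60 = 1.00, with both risks understated by 40%
- each arm anywhere from 50% to 100%: from 0.50 / 1.00 = 0.50 to 1.00 / 0.50 = 2.00

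This shows only that the direction is open and that equal capture removes the spurious difference. It does not estimate bias in this study.

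**The case against.** The best case for the plan is that this outcome is incidental. The objective, the hypothesis and the expected outcomes concern pain, analgesic use or both, and the outcome wording suggests reporting whatever turns up. No safety claim is planned. The Design section adds that an observational study does not change a patient's exposure to reactions. Acute events would mostly be seen under monitoring, and the open-ended clinical data list could include them.

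Much of this stands. It makes the priority minor and narrows the firm gap to an unnamed source, an unasked question at 24 hours and a missing summary. It does not close the gap. The plan chose to list adverse effects as an outcome, and managing a reaction is not the same as recording it for comparison.

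A reader might go further and infer any of the following. The documents do not support them.

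- *Adverse effects will not be recorded at all.* Monitoring makes charting of acute events likely, and the data list is not closed.
- *The comparison is biased for, or against, the block.* Neither direction nor size can be read from the plan.
- *The sponsor decided not to analyse adverse effects.* The analysis text may be missing from the supplied copy. If nothing was lost, no outcome has a stated method, and this omission is part of a wider gap.
- *Every named risk needed its own question.* Systemic toxicity and nerve injury are clinical findings, which a patient cannot reliably confirm with a yes or no by telephone.

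**Conclusion.** The point holds as a cheap improvement of minor priority. Adverse effects are a declared secondary outcome that no described assessment elicits, with no named source and no place in the Data Analysis sentence. Capture after PACU may be incomplete and, without blinding, may differ by arm in either direction. The effect is confined to this one secondary outcome.

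The conclusion assumes that the described assessments are the complete set of study contacts, and that any lost analysis text did not define how adverse effects are collected. If a case report form or a lost section does so, the point reduces to citing it in the protocol.

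**What to change.** 1. **24-hour call.** Add one short set of symptom questions, worded identically in both arms, on the patient-reportable events that the Design section already lists: for example nausea, vomiting, itching or rash, dizziness and fainting. State whether opioid side effects count as adverse effects.
2. **Source records.** Name the anesthesia record and the PACU record as the source for clinician-identified events (systemic toxicity, nerve injury, allergic reaction) from induction, a start time both arms share, to PACU discharge. Review them the same way in both arms.
3. **Data Analysis.** Add a descriptive by-arm count and proportion with 95% CI for any event and for each event type, counting each patient once per type. Give the number reached at 24 hours in each arm, so that the denominator for call-reported symptoms is visible. Describe the comparison as unblinded and non-randomised.

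**Cost.** A few extra questions on a call that is already planned, review of two existing records per patient, and a short addition to Data Analysis. No new contact is needed.

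**Limits.** Prompted questions will pick up more minor symptoms than charting alone. Reporting bias from the lack of blinding remains, and because the block follows surgeon preference and patient consent, any difference between arms stays descriptive. A clinician-identified event that first appears after PACU discharge would still be missed unless later hospital notes are also named as a source.

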Given the utility of the QL block in controlling somatic pain, this study aims to determine whether the QL block is an effective analgesic adjunct in the control of postoperative pain period, specifically with regards to patients undergoing laparoscopic gynecologic surgery.

STUDY OBJECTIVES

this study aims to determine whether the posterior QL blocks is an effective analgesic adjunct in the control of postoperative pain period, specifically with regards to patients undergoing laparoscopic gynecologic surgery.

HYPOTHESIS

The patients receiving QL blocks will have lower post-operative pain scores and will need less oral supplemental pain killers.

Subjects:

Women aged 18 to 65 presenting for scheduled laparoscopic or robotic total or supracervical hysterectomy for benign indication.

Eligibility Criteria:

Patient will be eligible for recruitment if between the ages of 18 to 65 scheduled to undergo laparoscopic or robotic total or supracervical hysterectomy for benign indications. Only surgery for benign pathology will be considered to enrollment. No Malignancy cases will be included.

Exclusion criteria:

1. History of adverse reaction or allergy to Bupivacaine or liposomal bupivacaine
2. Medical contraindication to placement of QL block.
3. Suspicion of possible reproductive cancer with contraindication of morcellation of uterine tissue.
4. Significant medical condition or laboratory result that in the opinion of the Investigator indicate an increased vulnerability to study subject which exposes the subject to an unreasonable risk as a result of participating.
5. Any clinically significant condition uncovered during the surgery, such as excessive bleeding or decompensation, that might render the subject medically unstable to continue the study or complicate the subject's intraoperative or postoperative course.

6. Pregnant patients
7. Less than 40Kg weight.

Design:

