Prospective Cohort observational study. All patients that meet criteria for participation in this study will be screened: patients scheduled to undergo a laparoscopic hysterectomy for benign conditions by attending physicians in the division of Minimally Invasive Gynecologic Surgery. Based on surgeon's preference, and patient's consent, the patient is offered a QL block or not. Our aim is to follow the patient's pain scores post op and amount of oral pain medication used whether they received QL block or not. If the patient received the QL block then they will be considered part of the study arm. If the patient did not receive the QL block then they will be considered part of the control arm.

The QL block is best thought of as a volume or compartment block in that volumetric spread of LA along the fascial plane is associated with efficacy in blocking the thoracolumbar nerves between T7-L1. It can be reasonably assumed that this compartment is the same across patients and is not affected by the amount of subcutaneous or central fat present in the obese patient.

If a block is to be performed, the QL block will be performed using a 21G x 100mm Stimuplex needle under ultrasound guidance using a curvilinear probe. Subjects will be positioned in the semi-lateral position to facilitate access into the plane posterior to the quadratus lumborum muscle and middle layer of thoracolumbar fascia. The QL block will be administered via an in-plane approach and local anesthetic will be injected between the quadratus lumborum muscle and the middle layer of the thoracolumbar. The QL block will be in the operating room after induction prior to starting the scheduled surgical procedure. If the block is performed, it will include 20ml of 0.25% bupivacaine and 5ml of liposomal bupivacaine (Exparel) per side. The block will be done bilaterally therefore **a total** of 40ml of 0.25% bupivacaine and 10ml of liposomal bupivacaine (Exparel) will be administered.

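### The medication comparison counts oral drugs only, although pain medication in the recovery unit is to be recorded without a route limit

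*Combined protocol and SAP*

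**What the plan says.** The combined protocol and SAP states the medication comparison in five places, each limited to the oral route:

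- Hypothesis: patients given the block "will have lower post-operative pain scores and will need less oral supplemental pain killers".
- Design: the aim is to follow pain scores and the "amount of oral pain medication used whether they received QL block or not".
- Secondary outcome (in the outcomes paragraph before Data Analysis): "difference in additional medication taken orally for pain control".
- Data Analysis: "the difference in the amount of oral pain medication used will be assessed as below".
- Expected Outcomes: block patients "will need less oral pain medication".

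Three statements describe what is observed or collected, and none limits the route:

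- Data Collection Procedures, opening paragraph: "post op pain scores and amount of pain medication used".
- Data Collection Procedures, PACU: "The amount, timing and type of additional pain medications necessary at 1 and 3 hours after surgery will be recorded".
- The 24-hour telephone call: patients are "asked about how much additional medication they have taken for pain control".

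The primary outcome is the difference in pain score at 3 hours.

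**The concern.** The outcome as defined is narrower than the data to be gathered, and no reason is given for the restriction. It also fits poorly with the study's rationale. The Introduction places the heavy analgesic need after laparoscopy in the first 4 hours, and the Background is concerned with reducing additional narcotic use. Neither is framed by route, and the Study Objectives ask whether the block is an effective analgesic adjunct without mentioning route.

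The 3-hour primary score lies inside that 4-hour window. If part of the rescue there is non-oral, an oral-only measure can miss a real difference in early analgesic need, or can show a difference that only reflects a shift from one route to another. The 3-hour pain difference under usual rescue is still a valid quantity, but its meaning depends on how much rescue each arm received beforehand, and the plan has no stated comparison of that total.

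This point is separate from confounding by surgeon preference and from rescue given by unblinded staff, which it does not address.

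**Working it through.** **1. The text, side by side.** The documents give no figure to reproduce here, so the first check is a count.

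| Kind of statement | Where | Limited to oral? |
|---|---|---|
| Comparison | Hypothesis | Yes |
| Comparison | Design (aim) | Yes |
| Comparison | Secondary outcome | Yes |
| Comparison | Data Analysis | Yes |
| Comparison | Expected Outcomes | Yes |
| Collection | Data Collection Procedures, opening paragraph | No |
| Collection | Data Collection Procedures, 1 and 3 hours | No |
| Collection | 24-hour call | No |

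The comparison is limited to oral drugs in 5 of 5 statements, and collection in 0 of 3.

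**2. Does anything close the gap?** Data Analysis points to a method below it, but only Expected Outcomes and the reference list follow. No passage says how non-oral drugs would be handled, gives a unit for adding amounts of different drugs, or sets a time window for the medication outcome.

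**3. Possible size.** Every number in this step is an assumption chosen for illustration. Let control-arm use over 0–3 h be T = 20 morphine-equivalent units, let the block reduce use by r = 0.30 equally across routes, and let p be the non-oral share.

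- All-route difference: T × r = 20 × 0.30 = 6.
- Oral-only difference: T × (1 − p) × r.

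| p | Oral-only difference | Share of the 6 missed |
|---|---|---|
| 0 | 6 | 0% |
| 0.25 | 4.5 | 25% |
| 0.50 | 3 | 50% |
| 0.75 | 1.5 | 75% |
| 1 | 0 | 100% |

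**4. Shift of route with equal totals (assumed).** Both arms use 20 units; the non-oral share is 75% in control and 50% in the block arm.

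- Control, oral: 20 × (1 − 0.75) = 5.
- Block, oral: 20 × (1 − 0.50) = 10.
- Oral-only difference, control minus block: 5 − 10 = −5. True difference: 20 − 20 = 0.

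The block arm appears to use 5 units more when total use is the same. With the two shares exchanged, the result is 10 − 5 = +5, an apparent saving that does not exist. The error can go in either direction.

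**The case against.** The strongest reply is that the documents show no harm. They name no postoperative analgesic and no route, and if all PACU rescue is oral, nothing is lost. Recording more than one compares is not a contradiction, and five consistent uses of the oral limit may reflect a deliberate choice. On that reading the outcome is a narrower quantity, not a biased one.

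Several parts of this stand:

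- Non-oral rescue is an assumption, and the illustrative amounts have no source in the documents.
- Under an equal reduction across routes, oral use still falls by 30% at every non-oral share below 100%. Only the absolute difference shrinks. A misleading direction needs a shift of route between arms.
- The medication outcome has no stated window. If it was meant to cover 24 hours and later use is mostly oral, the missed share would be smaller than in the 0–3 h illustration.
- The Design sentence could be read as describing follow-up instead of a comparison. The counts would then be 4 of 4 comparison statements limited to oral and 1 of 4 collection statements so limited. The mismatch remains.
- The missing analysis method and common unit are separate gaps. They would remain if the oral limit were removed, and they add no weight to the route point.

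The reply does not remove the concern. The collection text would capture non-oral rescue, and the outcome definition, followed as written, would discard it. If the limit is deliberate, the plan gives no reason for it and does not say what happens to the remaining data. If it is loose wording, leaving it in place allows the choice between oral-only and all-route totals to be made after the data are seen.

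**Conclusion.** The concern holds. Every statement of the medication comparison is limited to oral drugs, the planned collection is not, and any non-oral PACU rescue would fall outside the stated comparison. That mismatch is certain from the text. Its consequence depends on a rescue regimen that the documents do not describe: the loss could be nil if all rescue is oral, or the whole absolute difference if none is, and a different route mix between arms could create a spurious difference in either direction.

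The primary outcome is not invalidated. The effect falls on one secondary outcome, but that outcome carries the medication half of the hypothesis. The change should be made, with medium confidence in its practical importance.

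**What to change.** In the secondary outcome and in Data Analysis:

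- Define total additional analgesic use by any route, cumulative over 0–1 h and 0–3 h after surgery.
- Put opioids on a common morphine-equivalent scale, with the conversion table fixed in advance, and report non-opioids separately.
- State that the 1-hour and 3-hour records are cumulative, which the present text does not establish.
- Report the 0–3 h total by arm beside the 3-hour pain score.
- Keep oral use as a component.

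If the oral limit is intended, the minimum is to give the reason for it and say how non-oral use will be reported. That would settle the wording but would still leave early total use uncompared.

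The cost is low for 0–3 h, because amount, timing and type are already to be recorded. Route is not a listed item and must be added or derived from the type of drug. Morphine-equivalent conversion is approximate, which should be acknowledged.

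Extending the total to 24 hours is optional and costs more. The telephone call would have to ask for drug name, strength and number taken, and medication given by staff after 3 hours would also have to be captured. None of this alters patient care; it changes only what is measured and reported.

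### The block is not randomized, no preoperative pain score is planned and only a mean difference is stated, so the 3-hour comparison may mix block effect with surgeon, case mix and prior pain

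*Combined protocol and SAP*

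**What the plan says.** The Design section describes a prospective observational cohort. The surgeon's preference and the patient's agreement decide whether a block is given, and the arms are defined by whether it was received. Data Collection Procedures confirms that "there will be no randomization or blinding done".

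In the same section, "Our primary outcome is difference in pain scores at 3 hours". The assessments follow surgery: "Pain levels will be documented at the same 1- and 3-hours intervals", with a telephone call at 24 hours. The medication records are postoperative too. No preoperative pain score and no preoperative analgesic use is listed.

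The covariates are introduced with "Sociodemographic and clinical data of study subjects will also be obtained, including age, body mass index, history of abdominal and pelvic surgeries". The list goes on to pelvic adhesive disease such as endometriosis, then "duration of surgery, and duration of stay postoperatively in PACU". The operating surgeon is not on it. No use in the analysis is stated for any item.

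Data Analysis names "the mean difference between pain scores at 1 hour, 3 hour, and 24 hour" and adds that "the difference in the amount of oral pain medication used will be assessed as below". Only Expected Outcomes and the references follow.

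**The concern.** Study Objectives asks whether the block is effective, and Expected Outcomes looks for lower scores in blocked patients. The 3-hour difference will therefore be read as an effect of the block. In a cohort where surgeon and patient choose, that reading requires the groups to be alike in whatever else drives early pain, or to be made alike in the analysis.

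Two things stand in the way. Pain before surgery is a natural predictor of pain after it, and it is not measured. No adjustment is stated for the covariates that are measured, or for the surgeon, whose preference the protocol names as a determinant of block use.

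The bias could go either way. More prior pain among blocked patients would hide a benefit; less would create one. The preoperative score is also the time-critical item: surgeon, route and type of hysterectomy can be read later from the operative record, but a score on the study's own scale cannot be reliably recovered after surgery.

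**Working it through.** The documents give no sample size, SD, alpha, test, target difference or block share, so there is no stated figure to reproduce. What follows is an illustration, and every input is an assumption. It models imbalance in preoperative pain only; it does not model surgeon effects.

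**Assumed inputs**
- Slope of 3-hour NRS on preoperative NRS: 0.2 to 0.5, centre 0.35.
- Between-group difference in mean preoperative NRS: 0.5 to 1.0 points, centre 0.75.
- SD of preoperative NRS 2; residual SD 2.
- Equal groups, nominal two-sided 5% test, no true block effect.

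**Formulas**
- Bias b = slope × imbalance.
- SD = sqrt(2² + slope² × 2²).
- SE = SD × sqrt(4/n), with n the total number of patients.
- False-positive rate = 1 − Φ(1.96 − b/SE) + Φ(−1.96 − b/SE).

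**Results**

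| Slope × imbalance | n | b | SD | SE | False-positive rate |
|---|---|---|---|---|---|
| 0.2 × 0.5 | 100 | 0.10 | 2.040 | 0.408 | 5.7% |
| 0.35 × 0.75 | 100 | 0.2625 | 2.119 | 0.424 | 9.5% |
| 0.5 × 1.0 | 100 | 0.50 | 2.236 | 0.447 | 20.1% |
| 0.35 × 0.75 | 60 | 0.2625 | 2.119 | 0.547 | 7.7% |
| 0.35 × 0.75 | 200 | 0.2625 | 2.119 | 0.300 | 14% |

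The bias does not shrink as patients are added. The SE does, so the error rate rises with n.

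**Allowance for the listed proxies.** Prior surgery and endometriosis partly stand in for prior pain. If adjusting for them removed 25% of the central bias, b = 0.2625 × 0.75 = 0.197 and the rate at n = 100 is 7.5%. If it removed 50%, b = 0.131 and the rate is 6.1%. With no imbalance, b = 0 and the rate is 5%.

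**Effect of adjustment.** In a simulation at n = 100 with slope 0.35 and a 1.0-point imbalance (the upper end of the range), the unadjusted bias was 0.35 and the error 12.8%. Adjusting for baseline NRS gave bias 0.00 and error 5.4%.

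**Interval width.** In the same setting, a model with baseline NRS and five further covariates simulated as balanced noise had an interval 1.03 times the unadjusted width at n = 60, 1.01 at 100 and 0.99 at 200. If the groups differ by 1 SD across all covariates together, the factor is sqrt(1 + 1/4) = 1.12 before any gain from explained variance. For surgeon terms it is sqrt(0.25/(p(1 − p))), where p is the block share among half the caseload and 1 − p among the other half (equal groups overall): 1.05 at p = 0.65, 1.25 at p = 0.8, and undefined at p = 1.

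**The case against.** **Nothing shows that prior pain drives block use.** This stands. The protocol names surgeon and patient choice, not pain. A reader might infer that blocked patients had more, or less, pain beforehand and that the result is therefore biased in a known direction. The documents support neither. Without the measurement, though, nobody can show that the groups were comparable.

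**The analysis text may have been lost.** This stands too. Data Analysis points forward to text that is not there. A reader might infer that the study has no adjustment plan; the document as supplied shows only that none is stated. If a missing section prespecifies adjustment, that part of the point falls. It still could not use a baseline score that was never taken.

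**Case mix is partly recorded.** Age, BMI, prior surgery and adhesive disease are collected, and the list is open-ended, so preoperative analgesic use could also be charted. The stronger reading, that the comparison cannot be separated from case mix, is therefore not supported. What can be said is that no use of these data is stated.

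**Anesthesia is common to all patients.** The Design section gives one regimen (for example, "analgesia will be provided with Fentanyl 2 mcg/kg"). That limits one source of difference between surgeons, but it does not balance the patients.

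**The size is not anchored.** Correct. Pairing the central slope with the largest imbalance would give 0.35 points and 13% at 100 patients, but that is not the middle of the range. Other assumptions would give other figures, and the documents offer no target difference against which to judge 0.26 points.

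**Conclusion.** The point holds in a limited form. The block is chosen, not randomized; every planned pain score is postoperative; and the only stated analysis is a mean difference. Followed as written, the 3-hour difference may combine block effect with surgeon, case mix and prior pain.

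Under the assumed range at 100 patients, this amounts to a bias of 0.10 to 0.50 points and a false-positive rate of 6% to 20%, with 0.26 points and 9.5% at the centre. The figures are lower if the listed proxies are used and remove part of the bias. They illustrate a mechanism and do not estimate what will happen in this cohort; direction and true size are unknown.

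The change should be made: the missing baseline score is plain from the text, the remedy is cheap, and the score cannot be reliably recovered later. Confidence is medium, because the importance of prior pain here is unknown and analysis text may be missing.

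**What to change.** **Collect.** Before premedication, record one NRS score on the same 1-10 scale and current analgesic or opioid use. Take surgeon code, route and type of hysterectomy from the operative record.

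**Analyse.** Supply the missing analysis text, with one prespecified adjusted comparison (regression or propensity-based) of 3-hour NRS as primary:
- Adjust for baseline NRS, preoperative analgesic use, age, BMI, prior abdominal or pelvic surgery, and endometriosis or adhesive disease.
- Include surgeon in the primary model where block use varies within surgeon.
- Do not adjust for PACU stay, and use duration of surgery only in a sensitivity model, since both follow the block.

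**Report.** Give the block rate by surgeon. If use is all-or-none or nearly so by surgeon, report the estimate as an association confounded with surgeon.

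**Cost.** Two preoperative questions, a few chart fields and one analysis paragraph. The interval is about 1-3% wider at 60-100 patients if the added covariates are balanced, and about 12% wider if the groups differ by 1 SD across the covariates together. Surgeon terms add about 5% at 65/35 block shares and 25% at 80/20, assuming mirrored shares and equal groups overall. The 12% and the surgeon figures are before any gain from explained variance. Adjustment also leaves confounding by anything still unmeasured.
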